#### 1.2.1 Primary endpoint: OS compared with external controls – 3 analyses

**Analysis #1: Overall survival in the whole patient population**: This analysis will evaluate the overall survival curves and median survival for all of the patients in the Trial (both ITT and PP populations). This analysis will compare the survival times of the 232 patients initially randomized to DCVax®-L to the selected external controls. The comparisons will include the following:

- an overall comparison of the 232 patients to all external control patients, pooled;
- a matching-adjusted indirect comparison (MAIC) that takes into account the distribution of prognostic factors between the 232-patient DCVax®-L trial population and the external controls, pooled;
- a MAIC of the 232 patients to the control patients of each individual external control trial.

All comparisons will include an overall curve comparison, as well as comparisons of survival percentages at certain time points (so-called milestone analyses).

Analysis #2: Conditional survival -- the "long tail": This analysis will evaluate specifically the "long tail" of survival in patients treated with DCVax®-L in this Trial. With immunotherapies, one of the features most focused upon and considered most important clinically is their capability to deliver greatly extended survival in a percentage of patients. This analysis will apply an established statistical methodology – conditional survival – to evaluate the survival tail in this Trial separately from the larger picture. This methodology will evaluate all of the survival data relating to patients who survived beyond a specified time threshold. (This time threshold is the "condition" or trigger of the analysis). By analysing all of the data from the time threshold onwards, this methodology evaluates the whole survival tail and provides a more complete and representative assessment than a landmark analysis which would only evaluate the status of the survival tail at a specific time point.

**Analysis #3: Survival in pre-specified sub-groups:** It has become well recognized that GBM patients may be categorized into distinct sub-groups based upon certain patient characteristics and/or tumor characteristics, and these distinct sub-groups have materially different survival with GBM. Such

SAP Version: 1.0

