OS ITT & PP procedure for log rank test  Sensitivity analyses: Internal to Study 020221  OS ITT & PP Cox PH Hazard ratio; landmarks  PFS ITT & PP Hazard ratio; landmarks  OS ITT & PP biomarker subgroup8 Hazard ratio; landmarks  PFS ITT & PP biomarker subgroup Hazard ratio; landmarks  Exploratory: Internal to Study 020221	cPFS 	ITT & PP	Cox PH	Hazard ratio; landmarks	5			
OS ITT & PP log rank test  Sensitivity analyses: Internal to Study 020221  OS ITT & PP Cox PH Hazard ratio; landmarks  PFS ITT & PP Hazard ratio; landmarks  OS ITT & PP biomarker subgroup  Hazard ratio; landmarks  PFS ITT & PP biomarker subgroup Hazard ratio; landmarks  Exploratory: Internal to Study 020221	PFS	ITT & PP	Karrison	Hazard ratio; landmarks	5			
OS ITT & PP Cox PH Hazard ratio; landmarks PFS ITT & PP Hazard ratio; landmarks OS ITT & PP biomarker subgroup  Hazard ratio; landmarks PFS ITT & PP biomarker subgroup Hazard ratio; landmarks  Exploratory: Internal to Study 020221	OS	ITT & PP		Hazard ratio; landmarks	5			
PFS ITT & PP Hazard ratio; landmarks OS ITT & PP biomarker subgroup  Hazard ratio; landmarks PFS ITT & PP biomarker subgroup Hazard ratio; landmarks  Exploratory: Internal to Study 020221	Sensitivity	analyses: Internal to Study 020221						
OS ITT & PP biomarker subgroup  Hazard ratio; landmarks PFS ITT & PP biomarker subgroup Hazard ratio; landmarks  Exploratory: Internal to Study 020221	OS	ITT & PP	Cox PH	Hazard ratio; landmarks	5			
PFS ITT & PP biomarker subgroup Hazard ratio; landmarks  Exploratory: Internal to Study 020221	PFS	ITT & PP		Hazard ratio; landmarks	5			
Exploratory: Internal to Study 020221	OS	ITT & PP biomarker subgroup 		Hazard ratio; landmarks	5			
	PFS	ITT & PP biomarker subgroup		Hazard ratio; landmarks	5			
TTP  ITT Hazard ratio; landmarks	Exploratory: Internal to Study 020221							
	TTP 	ITT		Hazard ratio; landmarks	5			

 $^{1}$   $\alpha$  5% 2 sided overall; accounting for interim analysis, final analysis to be conducted at  $\alpha$  2.409% 1 sided

<sup>2 Subjects randomized to DCVax®-L

<sup>3 Control arms from studies in newly diagnosed GBM identified in systematic literature review by independent experts, confirmed with independent neuro-oncology experts and further matched through MAIC

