#### 3.1.1 Overall survival

For the Primary Endpoint, analyses #1 (ITT Population) and #3 (Pre-Specified Sub-Groups), OS will be calculated from the date of randomization to the date of death due to any cause. If a subject is not known to have died at the date of database lock, that subject will be censored at the date the subject was last known to be alive. For these Primary Endpoint analyses, OS for subjects randomized to DCVax®-L will be compared to closely matched, independently determined external controls.

For Secondary Endpoint #1 (Post-Progression OS), OS will be calculated from the date of progression to the date of death due to any cause for subjects originally randomized to placebo who received DCVax®-L after crossover. If a subject is not known to have died at the date of database lock, then the death for that subject will be censored at the date that the subject was last known to be alive. For these Post-Progression OS analyses, the subjects who received DCVax®-L after crossover will be compared to matched external controls obtained from trials in recurrent GBM.

For Secondary Endpoint #4 (OS in the ITT population), OS will be calculated from the date of randomization to the date of death due to any cause or date the subject was last known to be alive in the same manner as for the Primary Endpoint analysis #1, except that the OS for subjects randomized to DCVax®-L will be compared to Within-Study controls (i.e. subjects randomized to placebo).

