#### 3.1.2 Conditional survival

For Primary Endpoint analysis #2 (Conditional survival or CS), survival will only be evaluated for subjects known to have survived to at least the observed median (M months OS) for subjects randomized to DCVax®-L. CS will be calculated from M months after the date of randomization to death due to any cause. If a subject is not known to have died at the date of database lock, the date the subject was last known to be alive will be used to calculate CS and will be considered censored [9].

Published data from other trials include OS at various time points and include Kaplan-Meier (KM) survival curves. The KM curves will be digitized and individual survival data will be derived from the digitized KM curves. In addition, access may be obtained to original data sets from some other trials. CS for subjects randomized to DCVax®-L in the Trial who survived to at least the observed median will be compared to matched external controls comprised of subjects who survived to at least the same time point (M months) in the other trials which have been selected by independent experts, confirmed with independent neuro-oncology experts and further matched through MAIC, pursuant to this SAP to serve as the comparison trials.

cPFS for subjects randomized to DCVax®-L will be compared to within-Study controls (i.e. subjects randomized to placebo).

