# 8.1.5 Comparison of treatments: if only published data are available for external studies

#### Primary analysis: simple proportional hazards models, external studies pooled

Where the original data are not available, the primary analysis will be a comparison between the reconstructed individual patient survival data reconstructed (by digitizing the published KM curves), for all subjects, pooled across the external studies, with the 232 subjects randomized to DCVax®-L. This analysis will include the published data from all of the studies independently selected to serve as controls for the Trial, regardless of whether they have been included with their IPD in the analysis above. For the MGMT methylated subgroup comparison, the individual patient data will be reconstructed for the external studies where the Kaplan-Meier curves are available for the subgroup (199 subjects in total for the 5 studies identified).

For the other subgroup comparisons, the individual patient data will be reconstructed for the external studies where the Kaplan-Meier curves are available for the subgroup. The following subgroups would be possible for the 5 studies identified to date, with the stated numbers of subjects (available from the external control populations) in each (see Table 3). Other subgroups may also be available if further studies are identified in the independent literature review. The subgroups will be analyzed in the following order:

•	MGMT promoter methylated	N = 199
•	Minimal residual disease	N = 210
•	Age < 65:	N = 184
•	MGMT unmethylated:	N = 349
•	Age >= 65:	N = 45
•	Significant residual disease:	N = 163

Overall survival

• The hazard ratio will be constructed for OS.

Survival conditional on survival to M months

The hazard ratio will be constructed for CS (conditional on survival to M months).

Overall survival for subgroups

- The hazard ratio will be constructed for OS for the MGMT methylated.
- The hazard ratio will be constructed for OS for other subgroups similarly where possible.

The confidence intervals for the hazard ratios will be constructed in line with the significance levels shown in Figure 3.

Job Number: 1555 Customer Reference: Study ID: 020221 SAP Version: 1.0

Kaplan-Meier estimates of the survival functions for the DCVax®-L population and the pooled comparator population will be plotted and estimates of survival (with 95% confidence intervals) at 6, 12, 18, 24, 30, 36, 42, 48, 54 and 60 months will be calculated.

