#### Sensitivity analysis 1: Matching-adjusted indirect comparison (MAIC), external studies pooled

A matching-adjusted indirect comparison (MAIC) will be used to compare the treatment groups. The MAIC technique is explained in detail in Appendix D.

Overall survival

The MAIC will be adjusted for the following characteristics.

Table 4: Characteristics to be matched via MAIC: selected studies

Characteristic	Number of studies	Cate	gories
MGMT methylation status	5	methylated	unmethylated
Performance status (KPS)	4	< 90%	>= 90%
Surgical status	4	Complete resection / minimal residual disease	Incomplete resection / significant residual disease
Sex	5	M	F
Race	4	White	Non-white
Age	5	Continuous	

The numbers of subjects in each subgroup will be calculated for each study where the information is available. For factors where the information is available for all external studies, the overall proportions across all 1,366 subjects can then be calculated. For factors recorded in only four out of the five studies, the proportion of subjects in those studies will be applied to all the 1,366 subjects for the purposes of matching.

For the pooled published studies, the reconstructed IPD will be compared to the weighted data resulting from matching (see Appendix D) from the DCVax®-L subjects. A Cox proportional hazards model will be used to estimate the treatment effect in the form of a hazard ratio.

Kaplan-Meier estimates of the survival functions for the weighted DCVax®-L population and the comparator population will be plotted and estimates of survival to 6, 12, 18, 24, 30, 36, 42, 48, 54 and 60 months will be calculated (with 95% confidence intervals).

Survival conditional on survival to M months

Conditional survival analysis using MAIC weights will not be feasible using published data, but will be conducted if original individual patient data are available.

Overall survival for subgroups

It may not be feasible to analyse survival in subgroups using the MAIC approach if the proportions of subjects with the relevant characteristics are not known for the subgroups unless the original data is available from comparator studies. If such data is available, this analysis will be conducted.

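### The SAP's endpoint definitions describe MAIC-matched external controls, but the tests that decide in 8.1.5 and 8.2.1 are unweighted pooled comparisons, with MAIC kept as a sensitivity analysis

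*Combined protocol and SAP*

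**What the plan says.** **Endpoint definitions.** Table 2 footnote 3 (newly diagnosed) and footnote 6 (recurrent) both describe the control arms as "confirmed with independent neuro-oncology experts and further matched through MAIC". Section 3.1.2 says of the conditional survival controls that they are "further matched through MAIC, pursuant to this SAP to serve as the comparison trials". Section 3.1.1 uses looser terms and does not name MAIC: OS for analyses #1 and #3 "will be compared to closely matched, independently determined external controls", and the post-progression subjects "will be compared to matched external controls obtained from trials in recurrent GBM".

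**Analysis sections.** Section 8.1.5 opens with "Primary analysis: simple proportional hazards models, external studies pooled", a Cox comparison of the 232 DCVax-L subjects with reconstructed data pooled across the external studies. It attaches the confirmatory levels to that analysis: "The confidence intervals for the hazard ratios will be constructed in line with the significance levels shown in Figure 3". The weighted version comes next, under the heading "Sensitivity analysis 1: Matching-adjusted indirect comparison (MAIC), external studies pooled". Sensitivity analysis 2 runs MAIC study by study and combines the results, with an upper limit at the alpha level of 8.1.1. In recurrent GBM, 8.2.1 makes an unweighted pooled Cox model primary, and 8.2.3 makes a study-by-study MAIC the sensitivity analysis.

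**Overview.** Section 1.2.1 lists "an overall comparison of the 232 patients to all external control patients, pooled" beside the pooled MAIC and the single-study MAICs under Analysis #1, without ranking them.

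**The concern.** The primary comparison is not randomized, so statistical adjustment is its main analytic protection against differences in case mix. The SAP itself treats age, extent of resection and performance status as prognostic and MGMT methylation as predictive of temozolomide response (Section 6), and accepts in 8.1.3 that no single external study supplies a perfectly matched population. A reader of Table 2 and Section 3 would take the confirmatory hazard ratio to be balanced on such factors. Under 8.1.5 it is not: any difference in MGMT status, residual disease, KPS or age between the 232 subjects and the 1,366 controls passes straight into the estimate that is tested. The unranked list in 1.2.1, and the confirmatory-level limit on a result labelled sensitivity, leave room for argument if the weighted and unweighted results disagree.

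**Working it through.** **1. The passages side by side.**

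| Endpoint | Definition of controls | Primary analysis | Role of MAIC |
|---|---|---|---|
| Analysis #1, OS | Table 2 fn 3: MAIC; 3.1.1: closely matched | 8.1.5: unweighted pooled Cox, Figure 3 levels | Sensitivity 1 (pooled) and 2 (per study, combined) |
| Analysis #2, conditional survival | Table 2 fn 3 and 3.1.2: MAIC | 8.1.5: unweighted pooled Cox | Sensitivity 1: not feasible with published data |
| Analysis #3, subgroups | Table 2 fn 3: MAIC; 3.1.1: closely matched | 8.1.5: unweighted pooled Cox | May not be feasible without original data |
| Secondary #1, recurrent OS | Table 2 fn 6: MAIC; 3.1.1: matched | 8.2.1: unweighted pooled Cox | 8.2.3: sensitivity, per study only |

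In no row does the primary analysis carry the matching in the definition. For conditional survival, the 3.1.2 definition cannot be carried out on the published-data route at all.

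**2. The plan's own figures.** Controls in Table 3: 411 + 229 + 374 + 43 + 309 = 1,366, as stated. Alpha in 8.1.1: 2% + 0.309% + 0.1% = 2.409%, as stated; Analysis #1 holds 2% of it. Control mix from Table 3: methylated 199/548 = 36% overall, but 122/376 = 32% in one study and 77/172 = 45% in the other; minimal residual disease 210/373 = 56%. Case mix does vary between the control sources.

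**3. How far an imbalance could matter (hypothetical).** The following are assumptions, not document figures:
- prognostic hazard ratios of 0.5 (methylated), 0.7 (minimal residual disease) and 0.75 (KPS 90 or more);
- about 200 DCVax-L and 1,150 control deaths;
- no true treatment effect.

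SE of log HR = √(1/200 + 1/1150) = 0.0766. One-sided 2% critical value = 2.054.

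Log-HR bias = share difference × (ln 0.5 + ln 0.7 + ln 0.75) = share difference × (−1.3375).

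P(pass) = P(Z > 2.054 + bias/0.0766).

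| DCVax-L share on each factor | Bias | Apparent HR | P(pass) |
|---|---|---|---|
| 5 points higher | −0.067 | 0.935 | P(Z > 1.18) = 12% |
| 10 points higher | −0.134 | 0.875 | P(Z > 0.31) = 38% |
| 5 points lower | +0.067 | 1.069 | P(Z > 2.93) = 0.2% |

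A second check starts from the apparent HR and assumes deaths in 70% to 90% of all 1,598 subjects. Case mix alone giving an HR of 0.95 leads to rejection in about 7–9% of trials; 0.90, about 21–26%; 0.85, about 45–55%.

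**4. What weighting costs.** With the effective sample (ESS) as a fraction of 232 and the same assumed deaths, HR needed = exp(−2.054 × √(1/(200 × ESS) + 1/1150)).
- 100%: SE 0.0766, HR 0.854
- 85%: SE 0.0822, HR 0.845
- 70%: SE 0.0895, HR 0.832

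**5. Whether the weighted test is already specified.** For Analysis #1, yes. Table 4 lists the factors, Sensitivity analysis 1 gives the Cox model, and Appendix D gives the weights, the robust standard error and the adjusted sample size. For recurrent GBM, no. In Table 7, age and sex are available for all ten studies, MGMT for five, KPS for five and race for three; resection is not listed.

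**The case against.** The best defence is that Section 8 governs. Section 1.2 sends the reader there for methods, and its headings separate primary from sensitivity analyses. Section 8.1.3 introduces MAIC as an addition to the control selection, as do the Executive summary and 1.1 for their matching methods, which is consistent with 8.1.5. That much stands: on a fair reading the unweighted Cox model decides. A reader might infer that the two analyses have equal standing and either could be cited as the planned one; the headings do not support that. The limit at the confirmatory level in Sensitivity analysis 2 still blurs the line.

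A reader might also infer that Table 2 prescribes a MAIC-weighted test. It does not. Its model column says only Cox PH, and footnote 4 refers to reconstructed data, with covariates if real data are available. The matching claim sits in the description of the controls. Nor does 8.2.1 itself assign alpha or label MAIC; those roles belong to 8.3.1 and 8.2.3.

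Section 8.1.4 does allow covariate adjustment if original data arrive. However, 8.1.5 still runs the unweighted comparison on published data from every study, and it is that analysis which carries the Figure 3 levels.

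MAIC is also no cure. Appendix D concedes an unverifiable assumption, and KPS, surgical status and race come from four of the five studies, with the proportions applied to all 1,366. Weighting balances measured factors only. Appendix D reweights the DCVax-L subjects towards the controls, so calling the controls matched is loose in any case.

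Finally, rewording the definitions to fit Section 8 would also remove the contradiction. That is so, but it would leave the main test of a non-randomized comparison unadjusted when an adjusted one is already written.

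**Conclusion.** The contradiction is real and lies within the current SAP: the endpoint definitions claim matching that the deciding analyses do not apply. It matters most for Analysis #1, which holds 2% of the 2.409% one-sided alpha and for which a weighted analysis is ready to use.

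The size of the bias is unknown. A reader might take the 12% and 38% as estimates of false-positive risk in this trial; they are not. They rest on assumed prognostic hazard ratios, assumed death counts and an imbalance in the same favourable direction on all three factors. The documents do not give the DCVax-L mix, and an imbalance the other way would make the unweighted test conservative. The figures show only that modest differences could matter, which is reason to settle the choice before unblinding.

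The remedy for Analysis #1 does not carry over unchanged to conditional survival, subgroups or Secondary Endpoint #1.

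**What to change.** Before unblinding, name one deciding analysis per endpoint.

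- **Analysis #1.** Make the pooled MAIC-weighted Cox model with robust standard error, now Sensitivity analysis 1, the deciding test at the Figure 3 level. Keep the unweighted pooled Cox model as a sensitivity analysis.
- **Conditional survival and subgroups.** Delete or qualify the MAIC wording in 3.1.2 and Table 2. State that these comparisons are unadjusted unless original data are obtained.
- **Secondary Endpoint #1.** Correct footnote 6 to agree with 8.2.1 and 8.2.3, since only per-study MAIC with uneven covariates is planned.
- **Sensitivity analysis 2.** State that its limit at the confirmatory level does not decide success.
- **Alignment.** Bring 1.2.1, Table 2, 3.1.1, 3.1.2, 8.1.5 and 8.2 into line.

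The cost is SAP wording plus some precision in Analysis #1: on the assumed deaths, the HR needed falls from 0.854 to 0.845 at 85% effective sample or 0.832 at 70%. The true effective sample is not in the documents; Appendix D already requires it to be reported.

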#### Sensitivity analysis 1: Matching-adjusted indirect comparison (MAIC), external studies pooled

A matching-adjusted indirect comparison (MAIC) will be used to compare the treatment groups. The MAIC technique is explained in detail in Appendix D.

Overall survival

The MAIC will be adjusted for the following characteristics.

Table 4: Characteristics to be matched via MAIC: selected studies

Characteristic	Number of studies	Cate	gories
MGMT methylation status	5	methylated	unmethylated
Performance status (KPS)	4	< 90%	>= 90%
Surgical status	4	Complete resection / minimal residual disease	Incomplete resection / significant residual disease
Sex	5	M	F
Race	4	White	Non-white
Age	5	Continuous	

The numbers of subjects in each subgroup will be calculated for each study where the information is available. For factors where the information is available for all external studies, the overall proportions across all 1,366 subjects can then be calculated. For factors recorded in only four out of the five studies, the proportion of subjects in those studies will be applied to all the 1,366 subjects for the purposes of matching.

For the pooled published studies, the reconstructed IPD will be compared to the weighted data resulting from matching (see Appendix D) from the DCVax®-L subjects. A Cox proportional hazards model will be used to estimate the treatment effect in the form of a hazard ratio.

Kaplan-Meier estimates of the survival functions for the weighted DCVax®-L population and the comparator population will be plotted and estimates of survival to 6, 12, 18, 24, 30, 36, 42, 48, 54 and 60 months will be calculated (with 95% confidence intervals).

Survival conditional on survival to M months

Conditional survival analysis using MAIC weights will not be feasible using published data, but will be conducted if original individual patient data are available.

Overall survival for subgroups

It may not be feasible to analyse survival in subgroups using the MAIC approach if the proportions of subjects with the relevant characteristics are not known for the subgroups unless the original data is available from comparator studies. If such data is available, this analysis will be conducted.

